4.4 Statistical Analysis Plan

All statistical tests use a type I error rate of 0.05. We will calculate descriptive statistics for all variables of interest including means, medians and standard deviations for continuous measures, and frequencies and percents for categorical variables. These calculations will be performed overall and stratified by treatment assignment. We will compare baseline characteristics between the treatment and retrospective groups. We will test for differences using independent samples t-tests (alternatively, Wilcoxon-Mann-Whitney tests if data are skewed) for continuous variables, and Chi-square tests (alternatively Fisher's exact tests if some cells are sparse) for categorical variables.

For the outcome of local recurrence rate (LRR) we will test the null hypothesis of no difference in the proportion of patients with local recurrence by catheter type using a Fisher's exact test.

For the outcome of tumor response measured as the change in enhancing tumor size (pretreatment – post treatment) we will evaluate changes at 1 month and 6 month separately. We will calculate the difference in tumor enhancement size at 1 month and 6 months using enhancement size at initial treatment as the reference group (i.e. we will have two continuous outcomes which can be positive or negative values). The analyses are exactly parallel for 1 month and 6 month outcomes. We will describe the approach for 6 months. We will fit a general linear model with Kenward-Roger denominator degrees of freedom. The outcome will be the first-differenced 6 month tumor enhancement size. We will use a random intercept to account for correlation between lesions within a given patient. The independent variables will include catheter type, age and sex. We will test the null hypothesis of no association between catheter type and change in tumor enhancement size. In the case that this model fails to converge, or in the case that most patients have only one tumor, we will use an alternative approach. In this alternative approach we will sample one lesion per patient and use ordinary least squares regression and include age and sex as covariates with catheter type as the primary predictor of interest. We will test the null hypothesis of no association between change in tumor enhancement size and catheter type. Should this model also fail to converge, we will simplify further and use a paired t-test comparing initial and 6 month tumor enhancement sizes in a sampled data set (i.e. one tumor per patient), or we will use a Wilcoxon-Mann-Whitney test if the sizes are skewed. We will test the null hypothesis of no association between catheter and tumor enhancement size change.

For the outcome of time to progression, we will quantify the number of weeks from treatment until tumor progression. Failures (or events) will be defined as progression of the tumor per CT examination or AFP level and extrahepatic disease by CT examination, or death due to complications related to the tumor. Censored observations will be defined as patients who we did not observe tumor progression, patients who were lost to follow up, or patients who had a

liver transplant before evidence of progression was found. For censored observations the time at risk will be calculated as the time from treatment initiation to the last known clinical encounter (for no progression or lost to follow up), or to liver transplant (for patients who had a liver transplant before evidence of progression was found); this will be measured in weeks. To test for differences in time to tumor progression between the treatment and the retrospective group, we will use Cox proportional hazards regression. Treatment group will be our primary predictor of interest, and we will include age, sex and a variable approximating stage/severity at time of treatment using homogenous groups. We will test the null hypothesis of no association between time to progression and treatment group.

For the outcome of survival time, we will quantify the number of weeks from treatment until death. Failures (or events) will be defined as death related to the tumor. Censored observations will be defined as patients who we did not die during the follow up period, or patients who were lost to follow up. For censored observations the time at risk will be calculated as the time from treatment initiation to the last known clinical encounter; this will be measured in weeks. To test for differences in survival time between the treatment and the control group, we will use Cox proportional hazards regression. Treatment group will be our primary predictor of interest, and we will include age, sex and a variable approximating stage/severity at time of treatment using homogenous groups. We will test the null hypothesis of no association between survival time and treatment group.

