2.1.4 High Recurrence Rates after standard TACE

The likelihood to achieve any response following TACE significantly depends on treatment, tumor number [66] and tumor size with radiologic Complete Response (CR) rates of up to 77% in tumors <2 cm in size but only 25% in tumors with diameters of >5 cm after the first TACE [68]. Similar size dependent differences in radiologic response also apply to repeated TACE sessions. While retreatment with multiple treatments shows a CR rate of 55% and 40% respectively in lesions <5 cm, CR rates are 25% and 0% in a tumor >5 cm. (12)

Furthermore, once complete radiologic response is achieved, overall 72% will suffer tumor recurrence after a median of 8.5 months of which 31% will present as local, 40% as distant intrahepatic and 27% a mixed (local and distant intrahepatic) relapse of disease and again, tumors >5 cm showed a significantly shorter time to recurrence (6 months, $p < 0.05$) (12)

Thus, typical patients requiring downstage have tumors > 5cm but have the poorest response rates requiring multiple procedures and hampered by a high recurrence rates.

2.1.5 Current Delivery Techniques with Standard Endhole catheters.

Currently the best results for TACE occur when the dose is delivered in a highly targeted manner into the tumor. Dense accumulation of embolic spheres or lipiodol into the tumor as documented by CT has been shown to have improved outcomes (13, 14). However, with standard endhole catheters achieving maximum delivery of embolic agents is limited by the development of stasis, non-target delivery and subsequently non target injury. Thus, often Interventional Radiologist use a crude angiographic endpoint of stasis or substasis as the current endpoint.

As DEB-TACE is performed through an endhole catheter with either stasis or substasis as an endpoint, this current methodology is extremely subjective, lacks a quantifiable endpoint and results in various degrees of embolization on patients. Thus, a significant variability on the delivery techniques and endpoints.

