2.4 Study Objectives

2.4.1 Purpose

The purpose of this study will be to prospectively evaluate the outcomes of patients with hepatocellular carcinoma (HCC) who undergo DEB-TACE with the Surefire Precision Infusion System for intentional effect of down-staging patients to OLT.

Patients with HCC and who are being evaluated for liver transplantation but outside Milan criteria and meet the eligibility criteria will be enrolled in the prospective single arm study.

Results of the prospective cohort will be compared to matched historical control patients who were previously treated with DEB-TACE, delivered with standard endhole catheters. This includes all patients treated at the University of Colorado since 2009 treated with 100-300 micron beads for whom follow-up is available.¹ The data are as follows.

	1-Month Response						
	[name] Criteria				Vesselle, G., et al. (2015) Range Criteria		
	0-3 cm	3-7 cm	>7 cm	Total	<5 cm	>=5 cm	Total
Count	84	60	8	152	129	23	152
Range	1.3-3.0 cm	3.2-7.0 cm	7.6-17.0 cm	1.3-17.0 cm	1.3-4.8 cm	5.0-17.0 cm	1.3-17.0 cm
Number Complete Response	33	15	0	48	47	1	48
Percentage Complete Response	39.29%	25.00%	0.00%	31.58%	36.43%	4.35%	31.58%
Number Partial Response	32	39	6	77	58	19	77
Percentage Partial Response	38.10%	65.00%	75.00%	50.66%	44.96%	82.61%	50.66%
Number Stable Disease	14	4	1	19	17	2	19
Percentage Stable Disease	16.67%	6.67%	12.50%	12.50%	13.18%	8.70%	12.50%
Number Progressive Disease	5	1	1	7	6	1	7
Percentage Progressive Disease	5.95%	1.67%	12.50%	4.61%	4.65%	4.35%	4.61%
Number Lost To Follow-up*	0	1	0	1	1	0	1
Percentage Lost To Follow-up*	0.00%	1.67%	0.00%	0.66%	0.78%	0.00%	0.66%
Total	84	60	8	152	129	23	152

¹ We have robust follow-up on these patients, which is the main reason that we are intending to use this historical comparator.

	6-Month Recurrence (Complete & Partial Response)						
	[name] Criteria				Vesselle, G., et al. (2015) Range Criteria		
	0-3 cm	3-7 cm	>7 cm	Total	<5 cm	>=5 cm	Total
Patients with Complete Response at 1-month	33	15	0	48	47	1	48
Number Lost To Follow-up at 6-months	2	3	0	5	5	0	5
Percentage Lost To Follow-up at 6-months	6.06%	20.00%		10.42%	10.64%	0.00%	10.42%
Number No Recurrence at 6-months	19	4	0	23	23	0	23
Percentage No Recurrence at 6-months	57.58%	26.67%		47.92%	48.94%	0.00%	47.92%
Number Recurrent Disease at 6-months	12	8	0	20	19	1	20
Percentage Recurrent Disease at 6-months	36.36%	53.33%		41.67%	40.43%	100.00%	41.67%
Subtotal	33	15	0	48	47	1	48

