4.3 Justification of Sample Size

The sample size for this study is based on the primary outcome of local recurrence rate (LRR). We conducted a power analysis to assess detectable difference in proportion recurring and the associated power for a Fisher' exact test. The test can be conceptualized by the following two by two table (2x2 plus margins are presented). We will test the null hypothesis of no difference in the proportion of patients with local recurrence by catheter type.

Tumor recurred	Endhole catheter	Precision catheter	Total
Yes	30 expected	?	30 + ?
No	70 expected	?	70 + ?
Total	100	50	150

Based on the existing literature, we expect our historical controls (endhole catheter) to have a local recurrence rate of 30%.³ The following table presents some possible scenarios for power and sample size. All of these estimates assume a 30% LRR in the control group and a type I error rate of 0.05. We have included sample sizes for the pilot phase of the study in the table below.. The pilot study will also include an interim analysis after treating at least 20 patients with the precision catheter. At this point we will compare the proportions of LRR in the control and comparison groups; although we do not expect statistical differences in LRR between the two groups due to low power, the funder has asked that we provide these data. This interim analysis will be solely used to provide a brief progress report to the funder; these interim data will not be published, nor will they be applied to any stopping rules for the study.

The data generated in this pilot study will be used to estimate power and sample size for a multicenterclinical trial.

Expected LRR: Endhole catheter	Expected LRR: Precision catheter	Detectable difference (absolute difference)	Type I error rate (alpha)	Power (1-beta)	N control group (Endhole catheter)	N comparator group (Precision catheter)
Pilot Phase						
30%	25%	5%	0.05	0.07	100	50

³ Thirty percent was selected as an anticipated amount to see an improvement in care. This seemed reasonable, given the current efficacy of therapy.

30%	20%	10%	0.05	0.21	100	50
30%	15%	15%	0.05	0.47	100	50
30%	10%	20%	0.05	0.78	100	50
Interim pilot phase analysis						
30%	25%	5%	0.05	0.05	100	20
30%	20%	10%	0.05	0.10	100	20
30%	15%	15%	0.05	0.21	100	20
30%	10%	20%	0.05	0.41	100	20

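### Local recurrence, the outcome that sets the sample size, is compared between non-randomised groups by an unadjusted Fisher test, so a tumour-size imbalance would be read as a catheter effect

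*Combined protocol and SAP*

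**What the plan says.** Section 4.3 sizes the study on LRR, with 100 endhole controls and 50 Surefire patients. It states "All of these estimates assume a 30% LRR in the control group and a type I error rate of 0.05".

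Section 4.4 gives LRR one analysis: "For the outcome of local recurrence rate (LRR) we will test the null hypothesis of no difference in the proportion of patients with local recurrence", comparing the two catheter types by Fisher's exact test. No covariate, stratum or weight is named. The same section plans a comparison of baseline characteristics but ties no action to an imbalance.

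Other outcomes are treated differently. For time to progression and for survival, Section 4.4 says "we will include age, sex and a variable approximating stage/severity at time of treatment using homogenous groups". The model for change in enhancing tumour size carries age and sex.

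On the choice of controls, Sections 2.4.1, 2.4.2 and 3.1 (with its footnote) call them matched. Section 3.3 says the 100 are a random sample. No matching variable or method appears anywhere.

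**The concern.** The groups are not randomised, so the comparison depends on matching or adjustment to make them alike. For LRR the plan specifies neither. A two-by-two test cannot separate the effect of the catheter from that of any prognostic factor distributed differently in the two groups.

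Tumour size is the obvious candidate. Section 2.1.4 reports that "tumors >5 cm showed a significantly shorter time to recurrence", and the control table in Section 2.4.1 shows more recurrence in the larger size class. The authors adjusted a secondary endpoint and survival for stage or severity, so they recognised the need in principle.

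The direction of any bias is open. Of the 152 historical patients, 129 had tumours under 5 cm. Sections 1.2 and 2.4.1 describe the Surefire patients as outside Milan, which would tilt the bias against the device. Inclusion criterion 3 in Section 3.5.2 also admits patients within Milan, so it could tilt the other way. Section 4.3 says these data will be used to size a multicentre trial, so a confounded difference would carry forward.

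**Working it through.** **1. The plan's own figure.** Section 4.3 gives power 0.78 for 30% against 10%, 100 against 50. Exact enumeration of Fisher's test with 0.025 in the tail gives 0.780, and the arcsine approximation with continuity correction gives 0.778. With the usual two-sided p-value it is 0.814. The power table is not the problem.

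**2. Recurrence by size** (Section 2.4.1, row "Number Recurrent Disease at 6-months", complete responders at 1 month):
- As printed: 12/33 = 36.4% at 0-3 cm and 8/15 = 53.3% at 3-7 cm; Fisher p = 0.35. Small-tumour share 33/48 = 69%.
- Among those followed (2 and 3 lost): 12/31 = 38.7% and 8/12 = 66.7%; Fisher p = 0.17. Small-tumour share 31/43 = 72%.

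**3. Expected LRR with no catheter effect.** If a share s of a group has tumours of 3 cm or less, LRR = s × p(small) + (1 − s) × p(large). The Surefire share is not in the documents; 35% is an assumption.
- Printed rates: controls 20/48 = 41.7%; Surefire 0.35 × 36.4 + 0.65 × 53.3 = 47.4%; difference 5.7 points.
- Followed rates: controls 20/43 = 46.5%; Surefire 0.35 × 38.7 + 0.65 × 66.7 = 56.9%; difference 10.4 points.
- All Surefire tumours small: differences of −5.3 and −7.8 points, an apparent benefit.

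**4. How many are evaluable.** Section 3.11 excludes patients with residual disease at 1 month from the six-month recurrence evaluation. At the historical complete-response rate of 31.58%, 0.3158 × 100 ≈ 32 controls and 0.3158 × 50 ≈ 16 Surefire patients remain (an assumption for the Surefire arm).

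**5. Fisher rejection rate with no catheter effect** (exact, two-sided, α = 0.05):

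| Surefire share ≤3 cm | Printed, 100 v 50 | Followed, 100 v 50 | Printed, 32 v 16 | Followed, 32 v 16 |
|---|---|---|---|---|
| Same as controls | 3.8% | 3.7% | 3.0% | 3.1% |
| 60% | 4.0% | 5.0% | 3.1% | 3.5% |
| 50% | 4.9% | 8.5% | 3.5% | 4.5% |
| 35% | 7.6% | 18.6% | 4.4% | 7.1% |
| 100% | 8.2% | 12.8% | 3.7% | 5.1% |

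**6. The stratified alternative.** In size stratum k, let b be Surefire recurrences, t all recurrences, m₁ and m₂ the control and Surefire counts, and n = m₁ + m₂. The Cochran-Mantel-Haenszel (CMH) statistic is [Σ(b − m₂t/n)]² / Σ[m₁m₂t(n − t)/(n²(n − 1))]. In 200,000 simulated trials per setting it rejects about 5% throughout the table. With continuity correction it rejects about 3% at 100 against 50 and 2% at 32 against 16.

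**7. Power for a true 20-point reduction** (followed rates, same simulation):

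| Setting | Fisher | CMH | CMH, corrected |
|---|---|---|---|
| 100 v 50, equal mix | 0.642 | 0.696 | 0.625 |
| 100 v 50, 35% small in Surefire | 0.18 | 0.61 | 0.53 |
| 32 v 16, equal mix | 0.19 | 0.27 | 0.16 |
| 32 v 16, 35% small in Surefire | 0.06 | 0.22 | 0.12 |

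**The case against.** The design names matching as its control for confounding, and matching on size would remove most of the bias modelled here. That would answer the point if a matching variable were given and Section 3.3 did not describe random sampling. As written, the matching cannot be relied on. The footnote to Section 3.1 also says the data will be used to develop a framework for comparison, but Section 4.4 already specifies the LRR test.

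The evidence on size is thin. The gradient rests on 48 complete responders and is compatible with chance. The table row counts recurrent disease without specifying local recurrence. The result in Section 2.1.4 covers local, distant and mixed recurrence and uses a 5 cm cut. This limits how exactly the bias can be sized. It does not remove the case for adjusting for a factor that the protocol itself treats as prognostic.

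A reader might go further and infer any of the following, none of which the documents support:
- That the Surefire arm will differ in size mix. Its mix is not reported, so an imbalance is plausible but not established.
- That size is the strongest known predictor of local recurrence. The documents rank no predictors.
- That stratifying never costs power. The apparent gain at equal mix comes from setting an uncorrected asymptotic test against a conservative exact one; with continuity correction, power is slightly lower than Fisher's.
- That stratifying rescues the endpoint. With about 32 and 16 evaluable patients, power is low under either test.

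**Conclusion.** The concern holds as a gap in the LRR analysis: nothing specified in the plan would keep a tumour-size imbalance out of the catheter comparison. Its size is conditional. With 35% small tumours in the Surefire arm against about 70% in controls, the spurious difference is about 6 to 10 points. Fisher's false-positive rate is then about 8% to 19% if all 150 patients are evaluable, and 4% to 7% if only about 32 and 16 complete responders are. The lower ends use the printed rates and the upper ends the followed-only rates. With 60% small tumours the rate does not exceed 5% in any setting. With few evaluable patients, the main harm is therefore a biased estimate and lost power, more than an inflated error rate. These figures assume a size mix that the documents do not give and size-specific rates from small numbers. The bias could hide a benefit or create one.

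**What to change.** Make the LRR analysis a CMH test stratified by baseline largest tumour diameter in two strata (3 cm or less, above 3 cm). If the strata are sparse, use Firth logistic regression with catheter and one size covariate; the likely number of evaluable patients does not support a longer covariate list. Report the size-standardised risk difference with a 95% confidence interval, and keep Fisher's test as a sensitivity analysis. State in advance whether a continuity correction is used. Reconcile the matched controls of Sections 2.4.1, 2.4.2 and 3.1 with the random sample of Section 3.3, naming the matching variables if there were any.

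The cost is mainly wording. Size is tabulated for the controls, and baseline CT or MRI is collected for the Surefire arm (Section 3.7), provided that the diameters were recorded before data entry stopped. The drawbacks are sparse strata and, with a continuity correction and equal size mix, a power loss of about two points. Because the study closed on 18 June 2018, the change should be reported as made after closure, with both analyses shown.

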1. STUDY OVERVIEW

1.1 Study Flowchart

1.2 Study Summary

Title	Bridge to Orthotopic Liver Transplantation (OLT) - (Surefire Precision vs Endhole Embolization with DEBTACE)
Short Title	SPEED 1
Protocol Number	16-1313
Phase	Phase IV – Post Market
Methodology	Single Arm Prospective
Study Duration	2 years
Study Center(s)	University of Colorado Hospital
Objectives	Prospectively evaluate the outcomes of patients with hepatocellular carcinoma (HCC) who undergo DEB-TACE with the Surefire Precision Infusion System for intentional effect of down-staging patients to OLT.
Primary Endpoints	
• Tumor Response (mRECIST criteria) at 1 month• Local recurrence rate (LRR) at 6 months
Number of Subjects	50
Diagnosis and Main Inclusion Criteria	Patients with HCC and who are being evaluated for liver transplantation but outside Milan criteria and have been prescribed DEB-TACE for tumor down-staging.
Study Product(s), Dose, Route, Regimen	DEB-TACE delivered with the Surefire Precision Infusion System

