2.4.2 Hypothesis

Delivery of DEB-TACE with the Surefire Precision Infusion System in patients with HCC who are being considered for liver transplant and are being treated for the purpose of tumor down-staging results in improved tumor response (mRECIST criteria) at 1 month as shown by contrast enhanced CT/MRI as compared to matched historical control patients who received DEB-TACE delivered with a standard endhole catheter.

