2.4.3 Primary Endpoints

1. Tumor response (modified RECIST criteria) at 1 month as shown by contrast enhanced CT/MRI. (Note: Tumor response will be determined on a per-treated lesion basis.)
2. Local recurrence rate (LRR) at 6 months as shown by contrast enhanced CT/MRI
3. Absolute Tumor enhancing maximum diameter at 1M and 6M.

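### Section 4.4 has no explicit test of 1-month mRECIST response, the endpoint of the stated hypothesis; what it tests as tumor response is absolute change in enhancing size

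*Combined protocol and SAP*

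**What the plan says.** **Hypothesis (2.4.2).** Using the Surefire catheter "results in improved tumor response (mRECIST criteria) at 1 month as shown by contrast enhanced CT/MRI", compared with matched historical controls.

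**Primary endpoints.** Section 1.2 lists two: "Tumor Response (mRECIST criteria) at 1 month" and local recurrence rate (LRR) at 6 months. Section 2.4.3 lists the same two and adds a third, "Absolute Tumor enhancing maximum diameter at 1M and 6M". Under the first it notes: "Tumor response will be determined on a per-treated lesion basis".

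**Definition (4.5.1).** mRECIST response is a category. CR is loss of arterial enhancement in all target lesions. PR is a fall of at least 30% in the sum of viable diameters. Progression is a rise of at least 20%. Stable disease is the remainder.

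**Analysis (4.4).** Outcome paragraphs cover four things:
- LRR, by Fisher's exact test;
- tumor response, in a paragraph that opens "For the outcome of tumor response measured as the change in enhancing tumor size": pre-minus-post enhancing size, at 1 and 6 months separately, in a linear model with catheter type, age, sex and a random intercept for patient;
- time to progression;
- survival.

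A general passage says "We will compare baseline characteristics between the treatment and retrospective groups" and then names t-tests or rank tests for continuous variables and "Chi-square tests (alternatively Fisher's exact tests if some cells are sparse) for categorical variables". It opens with "All statistical tests use a type I error rate of 0.05".

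**Sizing (4.3).** The sample size rests on LRR, and the study is called a pilot for a later multicenter trial.

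**The concern.** A reader who follows the hypothesis from 2.4.2 through 4.5.1 to 4.4 finds no test at the end. The quantity that 4.4 does test shares the name tumor response, but it is on another scale and answers another question. The study could report a catheter effect on centimetres of enhancement as if it settled a hypothesis about response categories. It could also choose a response level, CR or CR+PR, once the results are known.

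The two primary lists make this worse. Sizing points to LRR, the hypothesis points to response, 2.4.3 adds diameter, and nothing ranks the three. Because the data are meant to size a multicenter trial, an unclear response result would carry forward.

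**Working it through.** **1. Match each listed primary endpoint to a test in 4.4.**

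| Endpoint | In 1.2 | In 2.4.3 | Test in 4.4 |
|---|---|---|---|
| mRECIST response, 1 month | yes | yes | none explicit |
| LRR, 6 months | yes | yes | Fisher's exact |
| Enhancing maximum diameter, 1 and 6 months | no | yes | linear model on size change (by inference; 4.4 calls it tumor response) |

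The chi-square/Fisher sentence directly follows the baseline comparison, and LRR, also categorical, gets its own paragraph. The natural reading is that the sentence concerns baseline variables.

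**2. Compare the scales.** Percent change = decrease / baseline enhancing diameter, for a single lesion and a 2 cm decrease:
- 2 cm: 2/2 = 100%, no enhancement left, CR
- 4 cm: 2/4 = 50%, at least 30%, PR
- 8 cm: 2/8 = 25%, below 30%, stable disease

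The size-change model treats all three as the same outcome value, and baseline size is not among its covariates.

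**3. Does the response level need naming?** Controls, from the 1-month table in 2.4.1:
- CR: 47/129 = 36.4% below 5 cm; 1/23 = 4.3% at 5 cm or more. Fisher p = 0.0013.
- CR+PR: (47+58)/129 = 105/129 = 81.4%; (1+19)/23 = 20/23 = 87.0%. Fisher p = 0.77.

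CR depends strongly on tumor size, and CR+PR shows no such fall. The level therefore matters, and baseline diameter belongs in the model.

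**4. Reproduce the plan's own power figures.** Exact power is the sum, over all pairs of binomial counts, of the probability of those pairs with Fisher p ≤ 0.05. For LRR 30% against 25, 20, 15 and 10% at 100 and 50 patients, the doubled one-sided p gives 0.066, 0.197, 0.459 and 0.780. Section 4.3 prints 0.07, 0.21, 0.47 and 0.78. The minimum-likelihood version gives 0.079, 0.225, 0.502 and 0.814. The printed table is sound for the numbers it assumes.

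**5. Apply the same calculation to response.** The protocol states no power for it. Control rates are CR 48/152 = 31.6% and CR+PR (48+77)/152 = 125/152 = 82.2%, with one binary result per patient. Ranges run from the doubled to the minimum-likelihood version.

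| Gain | CR from 31.6% | CR+PR from 82.2% |
|---|---|---|
| 5 points | 0.07-0.08 | 0.08-0.10 |
| 10 points | 0.18-0.21 | 0.29-0.35 |
| 15 points | 0.37-0.40 | 0.76-0.81 |
| 20 points | 0.59-0.62 | not possible (82.2 + 20 > 100) |

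**6. Why 0.78 for LRR is not a yardstick.** Section 3.11 takes patients with residual disease at one month out of the 6-month recurrence evaluation, apart from the downstaging population. In the extreme case that only complete responders remain, at the control CR rate in both groups and with no exception applied, the numbers are 100 × 0.316 ≈ 32 and 50 × 0.316 ≈ 16. Power for 30% against 10% is then 0.21-0.27. The true evaluable number lies somewhere between this case and 100 and 50, and the documents do not fix it.

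**The case against.** **The generic categorical sentence could cover response.** It could be stretched that far, so the plan does not exclude a test. But the sentence would still name neither a level nor a unit.

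**The size model is not a stray analysis.** This stands. The plan says openly how it measures the outcome, the model fits endpoint 3 of 2.4.3, and its random intercept suits several lesions per patient. The fault is a loose label and an untested first endpoint, not an improper model.

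**The unit is already stated.** Largely so: the per-lesion note in 2.4.3 is specific to this endpoint and may reasonably govern over the general criteria in 4.5.1. One sentence would settle it.

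**LRR is the lead.** Section 4.3 does call it the primary outcome, and it is on both lists, so sizing on it is no contradiction. Still, 2.4.2 states the hypothesis on response, and no section ranks the endpoints.

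**It is a closed pilot.** Footnote 2 (at 3.5.2) says a comparison framework will be developed from the data, and the study closed on 06/18/2018. This limits the consequences. It does not supply the test, since 4.4 already specifies formal tests for other outcomes.

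Two stronger readings are tempting and not supported:
- A reader might infer from the control table that the choice of level would reverse a catheter comparison. The table compares tumor sizes within one catheter group, and one cell is 1/23. It shows that the level needs naming, nothing more.
- A reader might infer from 3.11 that 1-month response is the only efficacy result for most patients. The downstaging population is excepted there, and the documents do not give the non-excepted share.

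**Conclusion.** The point holds. Section 4.4 as written has no explicit between-catheter test of 1-month mRECIST response, although that is the stated hypothesis and the first primary endpoint on both lists. The analysis carrying the name tumor response measures absolute size change. The primary lists disagree, and no lead or order is declared.

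The conclusion about the missing test rests on the text alone. The power figures assume one result per patient, the full 100 and 50, and control rates equal to those in 2.4.1. The documents do not say how many 1-month responses existed at closure, so achieved power is unknown and could be lower. This should be corrected before any response result is presented as a test of the hypothesis.

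**What to change.** 1. **Add the test to 4.4.** Compare 1-month mRECIST response by catheter type at one named level, CR or CR+PR; the choice is the sponsor's. One example is a logistic model with catheter type and baseline tumor diameter, penalised if cells are sparse. Score per treated lesion as 2.4.3 notes, with clustering by patient, or state that the all-target-lesions definition in 4.5.1 governs.
2. **State which 1-month scan counts for retreated patients.** Keep this consistent with 3.11, which counts from the retreatment procedure, and apply the same rule to the controls.
3. **Relabel the size-change models** as the analysis of endpoint 3.
4. **Make 1.2 and 2.4.3 agree and name the lead endpoint or an order.** If LRR leads, reword 2.4.2 to match.
5. **State power for the response test**, for instance the figures above. Do not use 0.78 for LRR as a benchmark or describe it as unchanged.
6. **Date the amendment**, and label the analysis post hoc if outcomes have been seen.

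**Cost.** One amendment and one more analysis, with no new visits. Data entry stopped at closure, and the documents do not show whether per-lesion categories were recorded, so some abstraction from existing scans or records may be needed. Outcomes placed later in the order can no longer each be claimed at 0.05, and a choice made after outcomes were seen carries only post hoc weight.
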